5.7 Diet/Activity/Other Considerations

5.7.1 Diet

Subjects should maintain a normal diet unless modifications are required to manage an AE such as diarrhea, nausea or vomiting.

5.7.2 Contraception

ADXS11-001 may have adverse effects on a fetus in utero. Furthermore, it is not known if ADXS11-001 has transient adverse effects on the composition of sperm. Prior to enrollment, all male and female study candidates with reproductive potential must be advised of the importance of avoiding pregnancy during trial participation and the potential risk factors for an unintentional pregnancy. Women of childbearing potential is defined as females who have experienced menarche and who have not undergone successful surgical sterilization (hysterectomy, bilateral tubal ligation, or bilateral oophorectomy), are not postmenopausal (defined as amenorrhea ≥ 12 consecutive months or women on hormone replacement therapy with a documented serum follicle stimulating hormone level > 35 mIU/ml). Even women who are using oral, implanted, or injectable contraceptive hormones or mechanical products, such as an intrauterine device or barrier methods (diaphragm, condoms, spermicides), to prevent pregnancy, who are practicing

abstinence, and who have a sterile partner (eg, vasectomy) should be considered of childbearing potential.

All women of childbearing potential must have a negative pregnancy test within 72 hours prior to receiving ADXS11-001. The minimum sensitivity of the pregnancy test must be 25 IU/L or equivalent units of human chorionic gonadotropin. If the pregnancy test is positive, the patient must not receive ADXS11-001 and may not be enrolled in the study.

Male subjects may be enrolled if they are willing to use an adequate method of contraception. Women of childbearing potential may be enrolled if they are willing to use 2 methods of birth control. The 2 birth control methods can be 2 barrier methods or a barrier method plus a hormonal method to prevent pregnancy.

The following are considered adequate barrier methods of contraception: diaphragm, condom (by the partner), copper intrauterine device, sponge, or spermicide. Appropriate hormonal contraceptives will include any registered and marketed contraceptive agent that contains an estrogen and/or a progestational agent (including oral, subcutaneous, intrauterine, or intramuscular agents).

Subjects should be informed that taking the study medication may involve unknown risks to the fetus (unborn baby) if pregnancy were to occur during the study. In order to participate in the study all males and female study candidates of reproductive potential must adhere to the contraception requirement (described above) from Visit 1 through 120 days post last ADXS11-001 administration. If there is any question that a subject will not reliably comply with the requirements for contraception, that subject should not be entered into the study.

5.7.3 Use in Pregnancy

If a subject inadvertently becomes pregnant while on treatment, the subject will immediately be removed from the study. The site will contact the subject at least monthly and document the subject's status until the pregnancy has been completed or terminated. The outcome of the pregnancy will be reported to the Sponsor without delay and within 24 hours if the outcome is a SAE (e.g., death, abortion, congenital anomaly, or other disabling or life-threatening complication to the mother or newborn). The study investigator will make every effort to obtain permission to follow the outcome of the pregnancy and report the condition of the fetus or newborn to the Sponsor. If a male subject impregnates his female partner the study personnel at the site must be informed immediately and the pregnancy reported to the Sponsor and followed as described above and in [Section 7.2.2](#).

5.7.4 Use in Nursing Women

It is unknown whether ADXS11-001 is excreted in human milk. Since many drugs are excreted in human milk, and because of the potential for serious adverse reactions in the nursing infant, subjects who are breast-feeding are not eligible for enrollment.

5.7.5 Major and Minor Surgeries and ADXS11-001 Treatment

No formal studies of the effect of ADXS11-001 on wound healing have been conducted. However, based on its mechanism of action it is not expected that administration of ADXS11-001 would complicate wound healing. Therefore, a subject may initiate or resume study treatment 2 weeks after minor surgery (i.e. surgery involving little risk to the life of the patient; specifically an operation on the superficial structures of the body or a manipulative procedure that does not involve a serious risk) if the wound has completely healed and there are no wound healing complications. A subject who has wound healing complications following minor surgery, received major surgery or requires newly implanted artificial (prosthetic) joints, implants and/or devices which is permitted by the protocol during the course of the study, must wait a minimum of 6 weeks and must have recovered from any toxicity (e.g. return to baseline or Grade 1) and/or complication before the next infusion of study treatment. Sponsor consultation is required prior to resuming study treatment for these subjects. If the treatment is delayed due to concomitant surgery beyond 12 weeks the subject may be discontinued from the study.

On study, surgeries and/or procedures must be scheduled following the completion of 7 day course of prophylactic antibiotics post ADXS11-001 infusion. In addition, “recommended antibiotic prophylaxis” per institution standards for respective surgeries/and or procedures must be followed.

5.8 Withdrawal/Discontinuation Criteria

Subjects may withdraw consent at any time for any reason or be dropped from the trial at the discretion of the investigator should any untoward effect occur. In addition, a subject may be withdrawn by the investigator or the Sponsor if enrollment into the trial is inappropriate, the trial plan is violated, or for administrative and/or other safety reasons. Specific details regarding discontinuation or withdrawal are provided in [Section 7.1.5](#).

A subject can be discontinued from the treatment for any of the following reasons:

- Screen Failure
 - Adverse Event/Serious Adverse Event
 - Lost to Follow-Up
 - Disease Progression, radiographic and/or clinical
 - Death
 - Withdrawal of Consent by Subject
 - Investigator Decision/Study Non-Compliance by Subject
-

- Achieved Complete Remission
- Completed Study (maximum 24 months of study treatment)
- Other (specify)

In all cases, the reason for and date of withdrawal must be recorded in the eCRF and in the patient's medical records. The patient must be followed up to establish whether the reason was an AE, and, if so, this must be reported.

When a subject discontinues/withdraws prior to treatment completion, all applicable activities scheduled for the final assessment (End of Therapy assessments) should be performed at the time of discontinuation. Any AEs that are present at the time of discontinuation/withdrawal should be followed in accordance with the safety requirements outlined in [Section 7.2](#).

The investigator must make every effort to contact subjects who discontinue the study prematurely or are lost to follow-up and to schedule the end of therapy assessments. Attempts to contact such subjects must be documented in the patient's records (e.g., times and dates of attempted telephone contact, receipt for sending a registered letter).

5.9 Subject Replacement Strategy

Non-evaluable subjects will be replaced in order to achieve the total number of subjects.

5.10 Treatment after Initial Evidence of Radiologic Disease Progression

Immunotherapy may produce antitumor effects by potentiating endogenous cancer-specific immune response. The response patterns seen with such an approach may extend beyond the typical time course of responses seen with cytotoxic agents and can manifest as a clinical response after an initial increase in tumor burden or even the appearance of new lesions. If radiological imaging shows progressive disease (PD), subjects may continue on study with the option of continuing treatment, provided there is:

- no deterioration in ECOG performance status
- absence of signs and symptoms (including worsening of laboratory values) indicating disease progression
- absence of rapid progression of disease
- absence of progressive tumor at critical anatomical sites (e.g., cord compression) requiring urgent alternative medical intervention

Tumor assessment should be repeated ≥ 4 weeks later to confirm PD. If repeat imaging shows CR, partial response (PR) or stable disease (SD) compared to the baseline scan, treatments may be continued or resumed. If repeat imaging shows continued progression

of disease, subjects will be discontinued from study therapy, unless the basis for the PD assessment is enlarged tumor-draining lymph nodes in the presence of a target tumor reduction. In determining whether or not tumor burden has increased or decreased, Investigators should consider all target lesions as well as non-target lesions.

5.11 Clinical Criteria for Early Trial Termination

Early trial termination will be the result of the criteria specified below:

- Quality or quantity of data recording is inaccurate or incomplete
- Poor adherence to protocol and regulatory requirements
- Incidence or severity of adverse drug reaction in this or other studies indicates a potential health hazard to subjects
- Plans to modify or discontinue the development of the study treatment

In the event of Sponsor decision to no longer supply study treatment, ample notification will be provided so that appropriate adjustments to subject treatment can be made.

6 STUDY EVALUATIONS

6.1 Schedule of Events

Study Procedure	Screening ²	9 Week Treatment Cycle ¹									End of Therapy ³	Follow-Up
		Weeks										
		1	2	3	4	5	6	7	8	9		
Administrative Procedures												
Informed consent	X											
Eligibility Criteria / Subject ID Card	X											
Demographics/Medical History	X											
Prior Cancer History	X											
Prior/Concomitant Therapies & Procedures	X	X			X			X			X	X ⁴
Prophylactic Medication ⁶		X			X			X				
ADXS11-001 Administration ⁷		X			X			X				
Dispense/Prescribe Oral Prophylactic Antibiotics ⁸		X			X			X				X
Phone Call												X ^{4,5}
Clinical Procedures/Assessments												
Review Adverse Events ⁹	X	X			X			X			X	X ⁴
Vital signs/Weight ¹⁰	X	X			X			X			X	
Physical Examination	X	X			X			X			X	
ECOG Performance Status	X	X			X			X			X	
Laboratory Procedures/Assessments¹¹												
CBC with Differential	X	X			X			X			X	
Serum Chemistry Panel	X	X			X			X			X	
Coagulation Profile	X	X			X			X			X	

Study Procedure	Screening ²	9 Week Treatment Cycle ¹									End of Therapy ³	Follow-Up
		Weeks										
		1	2	3	4	5	6	7	8	9		
Urine Dipstick	X	X			X			X			X	
Urine Pregnancy Test ¹²	X	X			X			X			X	
Lm Surveillance Monitoring ¹³												X
Efficacy Measurements												
Tumor Imaging ¹⁷	X							X				

¹ Repeating 9-week treatment cycles. Study cycles will be numbered sequentially.

² Screening/Baseline tumor evaluations will be performed within 28 days prior to first dose of study treatment.

³ End of Therapy is not a visit. Assessments noted here must be completed upon the decision to discontinue a subject from study treatment.

⁴ Safety Follow-Up will be conducted via a telephone call *30 days (± 5 days) after the last ADXS11-001 infusion* to confirm the resolution of any new or ongoing adverse events and serious adverse events. All ongoing events must be followed through resolution.

⁵ Survival Follow-Up will be conducted at each visit during the *Lm Surveillance period* and via a telephone call *every 3 months (± 2 weeks) after the Lm Surveillance period* to determine survival status for all study subjects.

⁶ Subjects will be pretreated with prophylactic regimen at least [REDACTED] before each ADXS11-001 infusion.

⁷ The initial ADXS11-001 administration will identify Day 1 of Cycle 1. ADXS11-001 may be administered ± 7 days within each scheduled infusion.

⁸ All Subjects will receive a 7-day course of oral antibiotic therapy starting approximately 72 hours after administration of ADXS11-001. All subjects will also receive an additional 6 month oral antibiotic course to be initiated approximately 72 hours following the last dose of study treatment or anytime upon discontinuation of study treatment.

⁹ Adverse events and serious adverse events will be assessed from the time Informed Consent is obtained through 30 days after the last ADXS11-001 infusion is administered.

¹⁰ Height will be measured at screening only. Monitor vital signs immediately [REDACTED] for the first 4 hours following the completion of every ADXS11-001 infusion.

¹¹ CID1 Safety labs do not need to be repeated if screening labs are collected within 3 days of dosing. All laboratory procedures are to be completed and assessed by the investigator within 3 days prior to the administration of ADXS11-001 to confirm lab criteria for study treatment are met.

¹² Urine pregnancy tests must be performed within 72 hours prior to each ADXS11-001 infusion for female subjects of childbearing potential. If the urine test is positive or cannot be confirmed as negative, a serum pregnancy test will be required.

¹³ *Lm* Surveillance Monitoring will include a 6-month course of oral antibiotics and routine monitoring of CBC, CMP (including CRP, ESR) and blood cultures. Following completion of the last dose of study treatment or following study discontinuation, all assessments will be performed every 4 months (±2 weeks) for 3 years.

¹⁴ Baseline tumor imaging and assessments must be performed within 28 days prior to the first ADXS11-001 infusion in the first study cycle. Subsequent tumor imaging and assessments will be conducted at Week 8 (±1 week) for the duration of study participation. Radiologic progression, not accompanied by clinical deterioration, should be confirmed ≥4 weeks later.

7 TRIAL PROCEDURES

7.1 Trial Procedures

The Schedule of Events - [Section 6.1](#) summarizes the trial procedures to be performed at each visit. Individual trial procedures are described in detail below. It may be necessary to perform these procedures at unscheduled time points if deemed clinically necessary by the investigator.

Furthermore, additional evaluations/testing may be deemed necessary by the Sponsor for reasons related to subject safety. In some cases, such evaluation/testing may be potentially sensitive in nature (e.g., HIV, Hepatitis C, etc.), and thus local regulations may require that additional informed consent be obtained from the subject. In these cases, such evaluations/testing will be performed in accordance with those regulations.

7.1.1 Administrative Procedures

7.1.1.1 Informed Consent

The Investigator must obtain documented consent from each potential subject prior to participating in a clinical trial.

Consent must be documented by the subject's dated signature on the most current Institutional Review Board/Independent Ethics Committee (IRB/IEC) approved ICF document along with the dated signature of the person conducting the consent discussion.

A copy of the signed and dated ICF should be given to the subject before participation in the trial.

The initial ICF, any subsequent revised written ICF and any written information provided to the subject must receive the IRB/IEC's approval/favorable opinion in advance of use. The subject should be informed in a timely manner if new information becomes available that may be relevant to the subject's willingness to continue participation in the trial. The communication of this information will be provided and documented via a revised consent form or addendum to the original consent form that captures the subject's dated signature.

The informed consent will adhere to IRB/IEC requirements, applicable laws and regulations, and Sponsor requirements.

7.1.1.2 Eligibility Criteria

All inclusion and exclusion criteria will be reviewed by the investigator or qualified designee to ensure that the subject qualifies for the trial.

7.1.1.3 Subject Identification Card

All subjects will be given a Subject Identification Card identifying them as participants in a research trial. The card will contain trial site contact information (including direct telephone numbers) to be utilized in the event of an emergency. The investigator or qualified designee will provide the subject with a Subject Identification Card after the subject provides written informed consent.

7.1.1.4 Demographic/Medical History

Demographic information and a medical history will be obtained by the investigator or qualified designee. Medical history will include all active conditions and any condition that are considered to be clinically significant by the Investigator.

7.1.1.5 Prior Cancer History

The investigator or qualified designee will obtain prior and current details regarding disease status, including histopathologic confirmation of cancer, all prior cancer treatments and best response(s), if applicable (eg, systemic, radiation and surgeries).

7.1.1.6 Prior/Concomitant Therapies and Procedures

The investigator or qualified designee will review all prescription and nonprescription medication (excluding vitamins and nutritional supplements) taken by the patient from 28 days prior to screening and up to and including 30 days after the last administration of ADXS11-001; the information will be recorded in the medical record and on the eCRF. Any addition, deletion, or change in the dose of these medications will also be recorded. Generic names should be used to eliminate confusion that may result from trade names. Protocol-mandated prophylactic medications and antibiotics should also be captured in the eCRF.

7.1.2 Clinical Procedures/Assessments

7.1.2.1 Adverse/Serious Adverse Event Monitoring

The investigator or qualified designee will assess each subject to evaluate for potential new or worsening serious events from the time written informed consent is obtained through 30 days after the last ADXS11-001 dose is administered. Adverse experiences. Serious events experienced during this time will be graded, reported and recorded on the eCRF according to NCI CTCAE v 4.0 ([Section 12.2](#)). Toxicities will be characterized in terms regarding seriousness, causality, toxicity grading, and action taken with regard to trial treatment.

Please refer to [Section 7.2](#) for detailed information regarding the assessment and recording of AEs.

7.1.2.2 Physical Examination

The investigator or qualified designee will perform an evaluation by body system.

7.1.2.3 Vital Sign Measurement

The investigator or qualified designee will measure and record vital signs (including blood pressure, pulse rate, respiratory rate, and temperature) at Screening, prior to each ADXS11-001 administration and [REDACTED] for the first 4 hours following each infusion. Weight will be collected prior to each ADXS11-001 infusion. Height will be measured at screening only.

7.1.2.4 Eastern Cooperative Oncology Group Performance Scale

The investigator or qualified designee will assess ECOG status (see [Section 12.1](#)).

7.1.3 Laboratory Procedures/Assessments

Details regarding specific laboratory procedures/assessments to be performed in this trial are provided below. The total amount of blood to be drawn over the course of the trial (from pre-trial to trial discontinuation), including approximate blood volumes drawn by visit and by sample type per subject will be based on local laboratory requirements.

7.1.3.1 Laboratory Safety Evaluations

Laboratory tests for hematology, chemistry, urinalysis, *Lm* surveillance and others are specified in [Table 8](#).

Subjects must meet all lab criteria prior to dosing. Laboratory tests can be performed no more than 3 days prior to dosing. If screening laboratory tests are performed within 3 days prior to initial study treatment, they can be used for C1D1 labs. Results must be reviewed by the investigator or qualified designee and found to be acceptable prior to each dose of trial treatment.

Table 8 Laboratory Tests

Hematology	Chemistry	Urinalysis	Other
Hematocrit	Albumin	Blood	Serum β -human chorionic gonadotropin†
Hemoglobin	Alkaline phosphatase	Glucose	(β -hCG)†
Platelet count	Alanine aminotransferase (ALT)	Protein	PT (INR)
WBC (total and differential)	Aspartate aminotransferase (AST)	Specific gravity	aPTT
Red Blood Cell Count	Lactate dehydrogenase (LDH)	Microscopic exam (If abnormal)	Lm surveillance* blood cultures
Absolute Neutrophil Count	Carbon Dioxide ‡ (CO₂ or bicarbonate)	Urine pregnancy test †	
	Calcium		
	Chloride		
	Creatinine		
	C-Reactive Protein (CRP)*		
	Erythrocyte Sedimentation Rate (ESR)*		
	Glucose		
	Potassium		
	Sodium		
	Total Bilirubin		
	Direct Bilirubin (If total bilirubin is elevated above the upper limit of normal)		
	Total protein		
	Blood Urea Nitrogen		

† Perform on women of childbearing potential only. If urine pregnancy results cannot be confirmed as negative, a serum pregnancy test will be required.

‡ If considered standard of care in your region.

**Lm* surveillance Monitoring will include routine monitoring of CBC, CMP (including CRP, ESR) and blood cultures. Following completion of study treatment all assessments will be performed every 4 months (± 2 weeks) for 3 years.

7.1.4 Efficacy Measurements

7.1.4.1 Tumor Imaging and Assessment of Disease

CT and MRI will be considered the best currently available and reproducible methods to measure target lesions selected for response assessment. Conventional CT should be performed with contiguous cuts of 10 mm or less. Spiral CT scan should be performed using a 5 mm contiguous reconstruction algorithm (as a general rule, lesion diameter should be no less than double the slice thickness). Lesions on chest x-rays will be acceptable as measurable lesions when they are clearly defined and surrounded by aerated lung; however, CT is preferable. Ultrasound is not an acceptable method to measure disease.

Assessment of disease will be done using both RECIST 1.1 criteria and irRECIST criteria. All subjects who have completed one 9-week cycle of ADXS11-001 treatment will be considered evaluable for response.

7.1.4.2 Measurable and Non-Measurable Lesions and Disease

Measurable lesions will be those that can be accurately measured in at least one dimension with the longest diameter ≥ 2.0 cm (for spiral CT scan or MRI scan, ≥ 1.0 cm). Measurable disease will be present if the subject has 1 or more measurable lesions.

Non-measurable lesions/disease will be all other lesions (or sites of disease), including small lesions (those with all measurements < 2.0 cm or < 1.0 cm with spiral CT/MRI), or any of the following: bone lesions, leptomeningeal disease, ascites, pleural or pericardial effusion, lymphangitis, cutis/pulmonis, abdominal masses that are not confirmed and followed by imaging techniques, cystic lesions, and lesions occurring within a previously irradiated area unless they are documented as new lesions since the completion of radiation therapy.

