7.1.4.3 Target/Non-Target Lesions

All measurable lesions, up to a maximum of 2 per organ and 5 in total, should be identified as target lesions to be measured and recorded at baseline. The target lesions should be representative of all involved organs. Target lesions will be selected based on their size (the lesion with the longest diameter) and suitability for accurate repeated measurements. At baseline, a sum of the longest diameters for all target lesions will be calculated and recorded as the baseline tumor burden. The baseline sum will be used as the reference point to determine the objective tumor response of the target lesions.

Measurable lesions other than the target lesions and all sites of non-measurable disease will be identified as non-target lesions and will be recorded at baseline. Non-target lesions will be evaluated at the same time points as target lesions.

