7.1.4.4 Response in Measurable Lesions (RECIST 1.1)

At baseline, the sum of the longest diameters (SumD) of all target lesions (up to 2 lesions per organ, up to total 5 lesions) is measured. At each subsequent tumor assessment, the SumD of the target lesions and of new, measurable lesions (≥ 10 ; up to 2 new lesions per organ, total 5 new lesions) are added together to provide the total measurable tumor burden (TMTB):

TMTB = SumD target lesions + SumD new, measurable lesions

Percentage changes in TMTB per assessment time point describe the size and growth kinetics of both old and new measurable lesions as they appear. At each tumor assessment, the response in target and new measurable lesions is defined based on the change in TMTB.

- Complete Response (CR): Disappearance of all target lesions. Any pathological lymph nodes (whether target or non-target) must have reduction in short axis to < 10 mm.
- Partial Response (PR): At least a 30% decrease in the sum of diameters of target lesions, taking as reference the baseline sum diameters.
- Progressive Disease (PD): At least a 20% increase in the sum of diameters of target lesions, taking as reference the smallest sum on study (this includes the baseline sum if that is the smallest on study). In addition to the relative increase of 20%, the sum must also demonstrate an absolute increase of at least 5 mm. (Note: the appearance of one or more new lesions is also considered progression).
- Stable Disease (SD): Neither sufficient shrinkage to qualify for PR nor sufficient increase to qualify for PD, taking as reference the smallest sum diameters while on study.

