7.1.4.5 Immune-Related Response in Measurable Lesions (irRECIST)

In addition to evaluation using RECIST 1.1 criteria, an immune response adaptation of RECIST will be applied to this trial. The essential differences between irRECIST and RECIST criteria are as follows:

- New measurable lesions do not necessarily constitute progressive disease and they should be added into the total tumor burden. New non-measurable lesions do not constitute disease progression but will prevent the determination of an irCR.

- Apparent disease progression should be confirmed after 4 weeks in the absence of symptoms consistent with clinical deterioration.

At baseline, the sum of the longest diameters (SumD) of all target lesions (2 per organ and 5 in total) is measured. At each subsequent tumor assessment, the SumD of the target lesions and of new, measurable lesions (≥ 10 mm [lymph nodes ≥ 15 mm in shortest diameter]; up to 2 new lesions per organ, total 5 new lesions) are added together to provide the total measurable tumor burden (TMTB):

$TMTB = \text{SumD target lesions} + \text{SumD new, measurable lesions}$

Percentage changes in TMTB per assessment time point describe the size and growth kinetics of both old and new measurable lesions as they appear. At each tumor assessment, the response in target and new measurable lesions is defined based on the change in TMTB (after ruling out irPD) as follows:

Complete Response (irCR): complete disappearance of all target and new, measurable lesions, with the exceptions of lymph nodes which must decrease to < 10 mm in short axis

Partial Response (irPR): decrease in TMTB $\geq 30\%$ relative to baseline (see below)

Stable Disease (irSD): not meeting criteria for irCR or irPR, in absence of irPD

Progressive Disease (irPD): increase in TMTB $\geq 20\%$ relative to nadir

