7.1.4.6 Response in Non-Measurable Lesions (RECIST 1.1)

While some non-target lesions may actually be measurable, they need not be measured and instead should be assessed only qualitatively.

- Complete Response (CR): Disappearance of all non-target lesions and normalization of tumor marker level. All lymph nodes must be non-pathological in size (< 10 mm short axis).
- Non-CR/Non-PD: Persistence of one or more non-target lesion(s) and/or maintenance of tumor marker level above the normal limits.
- Progressive Disease (PD): Unequivocal progression of existing non-target lesions. (Note: the appearance of one or more new lesions is also considered progression).

When the patient also has measurable disease, to achieve ‘unequivocal progression’ on the basis of non-target disease, there must be an overall level of substantial worsening in non-target disease such that, even in presence of SD or PR in target disease, the overall tumor burden has increased sufficiently to merit discontinuation of therapy.

In the event that the patient has only non-measurable disease, the same general concepts apply as noted above, however, in this instance there is no measurable disease assessment

to factor into the interpretation of an increase in non-measurable disease burden. Because worsening in non-target disease cannot be easily quantified, a useful test that can be applied when assessing subjects for unequivocal progression is to consider if the increase in overall disease burden based on the change in non-measurable disease is comparable in magnitude to the increase that would be required to declare PD for measurable disease (ie, an increase in tumor burden representing an additional 73% increase in ‘volume’ which is equivalent to a 20% increase diameter in a measurable lesion).

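### Lymph nodes enter the target set and the sum by longest diameter but are judged for complete response by short axis, so a node already below the nodal CR size can be a target lesion

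*Combined protocol and SAP*

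**What the plan says.** **Measurability.** Section 7.1.4.2 states: "Measurable lesions will be those that can be accurately measured in at least one dimension with the longest diameter ≥ 2.0 cm". The cut drops to 1.0 cm "for spiral CT scan or MRI scan". Lymph nodes are not excepted, and they do not appear in the section's list of non-measurable lesions. A single lesion is enough: "Measurable disease will be present if the subject has 1 or more measurable lesions".

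**Selection and sum.** Section 7.1.4.3 ranks candidates on the same axis, "Target lesions will be selected based on their size (the lesion with the longest diameter) and suitability for accurate repeated measurements", and forms the sum on it: "At baseline, a sum of the longest diameters for all target lesions will be calculated and recorded as the baseline tumor burden". Sections 7.1.4.4 and 7.1.4.5 repeat the longest-diameter sum. Table 9 defines RECIST 1.1 partial response (PR) as a fall of at least 30% in it.

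**Nodal response.** Under CR, Section 7.1.4.4 says: "Any pathological lymph nodes (whether target or non-target) must have reduction in short axis to < 10 mm". Section 7.1.4.5 uses the same 10 mm short-axis limit for irCR, worded as an exception to complete disappearance. Section 7.1.4.6, on non-target disease, says: "All lymph nodes must be non-pathological in size (< 10 mm short axis").

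**The one nodal size rule for measurability.** Section 7.1.4.5 has it, for new lesions under irRECIST only: "lymph nodes ≥ 15 mm in shortest diameter".

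Inclusion criterion 5 (Section 5.1.1) and Section 12.3 refer to RECIST 1.1 by name. Neither writes out a rule for nodes at baseline.

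**The concern.** A node is admitted and summed on its long axis, then judged for CR on its short axis. The two can disagree. A long, thin node can pass the size test for a target lesion while being, by the plan's own limit, non-pathological. A node can also shrink across its short axis enough to meet the CR condition while the sum hardly moves.

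RECIST 1.1 response is a primary efficacy measure. Progression is read from the same sum and feeds 6-month PFS, the other primary measure. The trial is open-label (Section 5.2.7), and the only central review mentioned is for exploratory volumetric analysis (Section 12.3). The documents therefore describe no central reading that would settle which axis applies, and two sites could score the same node differently while each follows a written sentence.

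**Working it through.** The plan gives no figure on this point to reproduce. The check applies its written size rules to example nodes. The node sizes (long x short axis, mm) are illustrative assumptions.

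**Step 1. Classify.** Rules: measurable if long axis is at least 10 (spiral CT/MRI) or at least 20 (otherwise), from 7.1.4.2; non-pathological if short axis is under 10, from 7.1.4.6; new-node rule, short axis at least 15, from 7.1.4.5.

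| Node | Measurable, spiral/MRI | Measurable, other | Short axis < 10 | Short axis ≥ 15 |
|---|---|---|---|---|
| 12 x 8 | yes | no | yes | no |
| 14 x 8 | yes | no | yes | no |
| 18 x 9.5 | yes | no | yes | no |
| 22 x 9 | yes | yes | yes | no |
| 14 x 12 | yes | no | no | no |
| 20 x 15 | yes | yes | no | yes |

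The first four rows are measurable and already non-pathological in size. The 22 x 9 mm node shows that the overlap also exists at the 2.0 cm cut.

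**Step 2. A 14 x 8 mm node as sole target.** The baseline sum is 14 mm. The nodal CR size is met before treatment (8 < 10). PR needs a sum of 0.7 x 14 = 9.8 mm or less, a change of 4.2 mm.

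**Step 3. A node going from 20 x 12 to 18 x 9 mm.** Sum: (20 - 18)/20 = 10%, short of the 30% for PR. Short axis: 9 < 10, so the nodal CR condition is met. As sole target, the sum points to stable disease (SD) and the nodal sentence to CR. Now add a 10 mm non-nodal target that disappears. The sum goes from 30 to 18, and (30 - 18)/30 = 40%. That is PR on the sum, so the choice is between PR and CR and the response rate does not change. In this example the axis decides responder status only when the node is the sole target.

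**Step 4. Direction.** Put an unchanged node of 12 mm long axis beside a 30 mm lesion. PR needs a fall of 0.3 x (30 + 12) = 12.6 mm, and 12.6/30 = 42% of the lesion instead of 30%. Here the rule works against a response. In Step 3 the nodal sentence works in favour of one.

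**Step 5. Weight at the Stage 1 gate.** One subject is 1/31 = 3.2 points. Against the 10% response criterion, 3/31 = 9.7% fails and 4/31 = 12.9% passes. With n = 31 and a true rate of 10%, P(X ≥ 3) = 0.611 and P(X ≥ 4) = 0.376, so P(X = 3) = 0.611 - 0.376 = 0.235. That is the chance of finishing exactly one responder short. Section 8.2 also mentions a count of 3 or more; one subject is decisive at the margin under that cut too.

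**Step 6. Test the fix.** If a target node must start at 15 mm or more in short axis and is summed on that axis, reaching under 10 mm is a fall of more than (15 - 10)/15 = 33.3%. That exceeds the 30% PR cut, so for node-only targets the sum can no longer read SD when the nodal CR condition is met. Of the nodes in the table, only 20 x 15 mm remains measurable.

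**The case against.** The best defence is that RECIST 1.1 is adopted by name in inclusion criterion 5 and Section 12.3, so a site may apply that standard directly. This stands in part. Criterion 5 does not cite Section 7.1.4.2, and a reader who infers that a 14 x 8 mm node definitely qualifies a subject goes too far. It is unclear, because 7.1.4.2 is the only definition written out. The reference does not cancel the explicit longest-diameter instruction for all target lesions.

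A second defence is that a non-pathological node is not a lesion and never reaches the size test. That is a sensible reading, but no sentence requires it.

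A reader might infer that one scan always supports both SD and CR. Under irRECIST it does not, because irSD excludes anything meeting irCR. The ambiguity lies in Section 7.1.4.4, which asks for all target lesions to disappear and adds the nodal sentence without saying whether a target node must also disappear. Even there, every other target lesion must have gone.

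A reader might also infer that the progression nadir is wrong because the sum stays above zero at nodal CR. That does not follow: a 9 mm short axis would also leave a non-zero sum.

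Nor can a count of misclassified subjects be obtained by assuming a share with nodal targets. The documents give no share, and most such subjects would be scored the same way on either axis.

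Finally, the new-lesion threshold in Section 7.1.4.4 has lost its unit in the available text, so the absence of a nodal bracket there should carry little weight.

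**Conclusion.** The inconsistency is real and should be corrected. The plan states a longest-diameter rule for every target lesion and a short-axis rule for nodal CR, and they can disagree on the same node. This is a conflict between written rules, not merely missing detail.

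Its size cannot be computed from the documents: neither the number of subjects with nodal target lesions nor their node dimensions are given, and the bias can run either way. The largest supportable statement is that one reclassified subject moves the Stage 1 response rate by 3.2 points and could decide the response part of the gate. It would not necessarily decide whether Stage 2 opens, since a 6-month PFS rate of at least 20% also opens it. The conclusion assumes that Sections 7.1.4.2 to 7.1.4.6 are applied as written.

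**What to change.** - **Section 7.1.4.2:** state that a lymph node is measurable only if its short axis is at least 15 mm, the threshold Section 7.1.4.5 already uses for new nodes. Extending it to baseline is a choice the sponsor must make explicitly, because the documents now apply it only to new lesions under irRECIST. State also that nodes under 10 mm short axis are not counted as disease, and that inclusion criterion 5 is read with this definition.
- **Sections 7.1.4.3 to 7.1.4.5 and Table 9:** enter target nodes into baseline and follow-up sums by short axis, and all other lesions by longest diameter.
- **Section 7.1.4.4:** align the new-lesion text with Section 7.1.4.5.
- **Enrolled subjects:** re-derive the sums from existing scans.

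The documents name no class for nodes from 10 to under 15 mm, and none is proposed here; the sponsor should say how they are recorded.

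The cost is protocol and CRF wording and some re-measurement. A few small nodes would no longer count as target lesions.
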